## C.23. Patient Compensation

Participants will be paid \$15 for participation in each in person study data collection visits (total of 4). This payment may come in the form of cash reimbursement, electronic fund transfer, a VA check, or another form of payment through the VA. If the patient completes all in-person interviews they will receive a total payment of \$60. If a patient attends what would be the baseline study visit but cannot be enrolled because he or she has baseline blood pressure indicate hypertension is in control, the patient will be paid \$15 that corresponds to the baseline study data collection visit. Patients will not receive reimbursement for other contacts with study staff, including if they choose to participate in a qualitative interview at the end of the study. This payment is comparable to compensation in other related studies conducted at the Durham VAMC.

## D. DATA ANALYSIS.

The analysis plans outlined below will be used to addresses the study objectives. Specific statistical methods may be altered based on emerging understanding of statistical science.

### D.1. Data Summary

Descriptive statistics, including graphical displays (i.e., frequency distributions and box plots), will be used to summarize all study variables. We will construct individual and mean trajectory plots of the longitudinal outcome variables to understand their general trends over the study period. In addition, we will explore the variability and correlation structure of the longitudinal outcome variables.

### D.2. Analysis of Primary Hypothesis

**Veterans randomized to the titrated disease management intervention arm will have greater improvement in mean systolic blood pressure over the 18 months of follow-up than veterans randomized to the control arm.**

The purpose of the Primary Aim is to examine the impact of titrated disease management on mean systolic blood pressure over 18 months, and the trial is powered to detect a 5 mmHg difference between the two treatment arms (see sample size section D.3 below). As described above, blood pressure will be measured on all patients at baseline, 6, 12, and 18 months of follow up. A general linear model will be used to estimate changes in mean systolic blood pressure over time and test the primary hypothesis. Linear models are a flexible and powerful analytic tool for repeated continuous measures, such as systolic blood pressure.

The predictors in the model will include a time effect and the intervention-by-time interaction. We will use the results from our exploratory graphical methods as well as AIC and BIC fit indices to select the most appropriate way to model time for the two treatment groups over the 18 month follow up. In previous studies, we have generally observed a quadratic trend over time in the intervention group, where patients in the intervention group improve the first half of the study and sustain improvement for the remainder of the study. Other possibilities include a linear trend or categorical (i.e., dummy coded) time. The stratification

variables of baseline level of blood pressure control and diabetes status will also be included. A model with categorical time is shown below in equation (1):

$$SBP = \beta_0 + 6month*\beta_1 + 12month*\beta_2 + 18month*\beta_3 + 6month*IntArm*\beta_4 + 12month*IntArm*\beta_5 + 18month*IntArm*\beta_6 + baselineBPcontrol*\beta_7 + diabetes*\beta_8 + \epsilon$$

We will use our exploratory descriptive and graphical methods for variability and correlation as well as AIC and BIC fit indices to determine an appropriate covariance structure for to take into account the within-patient correlation between repeated measures over time. In previous studies, we have found that either a random intercept-slope (i.e., growth curve model) specification for the random effects or an unstructured covariance matrix has been most appropriate.

We will estimate the parameters in the model using the SAS procedure MIXED and contrasts will be written in the context of this model to test the treatment difference at month 18. Furthermore, if the intervention-by-time terms in the model are significant, this provides evidence that the difference in systolic blood pressure between the two treatment groups over the 18 months of follow up is not constant, that is, it is time-dependent. This is an omnibus test contrasting the two treatment groups at the 6, 12, and 18 month time points. If this interaction test is significant and if it represents a qualitative, rather than a quantitative effect, this will provide insight into the different time-dependent patterns for each intervention group. As a summary, model estimated means and confidence intervals of systolic blood pressure will be generated at each time point for both treatment groups. Additionally, simultaneous confidence intervals on the treatment group differences will be generated for each time point.

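### The form of time in the primary model is chosen from the trial's own data with no rule for ties, and the interaction test is misread as evidence of a changing effect

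*Protocol*

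**What the plan says.** Section D.2 models SBP at baseline, 6, 12 and 18 months with time, arm-by-time and the stratification variables. The form of time is to come from the exploratory graphs together with "AIC and BIC fit indices to select the most appropriate way to model time for the two treatment groups". Section D.1 shows that these graphs use the trial's own outcomes: "We will construct individual and mean trajectory plots of the longitudinal outcome variables to understand their general trends over the study period". D.2 says that earlier studies tended to show a quadratic trend in the intervention group, then adds: "Other possibilities include a linear trend or categorical (i.e., dummy coded) time". Equation (1) is offered as the categorical example, not as the default. The covariance structure is chosen in the same way.

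The primary contrast depends on the outcome of that choice: "contrasts will be written in the context of this model to test the treatment difference at month 18".

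On the interaction, D.2 takes significant arm-by-time terms as a sign that the gap in SBP separating the arms "over the 18 months of follow up is not constant, that is, it is time-dependent". The next sentence says: "This is an omnibus test contrasting the two treatment groups at the 6, 12, and 18 month time points". D.2 also plans that "simultaneous confidence intervals on the treatment group differences will be generated for each time point".

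**The concern.** There are two separate faults.

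**(a) Open model choice.** The three forms of time weight the visits differently when they estimate the month-18 difference. Unless the true curve fits the chosen form, they estimate different quantities. The plan settles the form after the outcomes have been seen, by three criteria (plots, AIC, BIC) that can conflict, and does not say which one decides. The estimator behind the primary p-value therefore stays open.

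**(b) Misread test.** The model has no arm main effect, so beta4, beta5 and beta6 in equation (1) are the arm differences at 6, 12 and 18 months. Testing them jointly against zero asks whether there is any difference at any visit. The omnibus sentence says so, yet the sentence before it takes significance as evidence that the difference changes over time. A steady benefit would be reported as time-dependent. That matters here because intensity is re-titrated at 6 and 12 months (section C.9.b) and readers will want to know whether the effect lasts. If linear time is chosen there is a single interaction coefficient, and the interaction test and the month-18 test are the same test.

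**Working it through.** **Inputs from section D.3:** 200 per arm, SD 17.5 mmHg, correlation 0.4 between time points, 15% attrition, 5 mmHg difference, 80% power, type I error 5%. **Assumed:** two-sided testing, SD 17.5 and correlation 0.4 at all visits, and the mean profiles named below. Unless stated otherwise, the stratum terms are left out.

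**The plan's own figure.** ANCOVA SD = 17.5 × √(1 − 0.4²) = 16.04. Per arm, n = 2 × (1.96 + 0.8416)² × 16.04² / 5² = 161.5, so 162. With attrition, 162 / 0.85 = 190.6, so 191 per arm and 382 in total. The stated 400 is on the safe side: 170 evaluable per arm give SE = 16.04 × √(2/170) = 1.74 and 82% power.

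**(a) What each form estimates at month 18** (170 complete per arm). Write d6, d12, d18 for the arm differences and t = (0, 1, 2, 3). The linear form gives 3 × t′V⁻¹d / t′V⁻¹t, where V⁻¹ is proportional to I − cJ and c = 0.4 / (1 + 3 × 0.4) = 0.1818. For a constant difference d, the numerator is 6d − 0.1818 × 6 × 3d = 2.727d and the denominator is 14 − 0.1818 × 36 = 7.4545. The month-18 estimate is therefore 3 × 2.727d / 7.4545 = 1.098d. The same algebra gives the other rows:

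| Form | Expected month-18 estimate | True constant −5 | SE | Power |
|---|---|---|---|---|
| Linear | −0.04 d6 + 0.37 d12 + 0.77 d18 | −5.49 | 1.62 | 92% |
| Quadratic | −0.22 d6 + 0.22 d12 + 0.93 d18 | −4.64 | 1.68 | 79% |
| Categorical | d18 | −5.00 | 1.74 | 82% |

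Simulation with an ML unstructured covariance agrees: −5.48, −4.65, −5.01, with power 91.8%, 79.1%, 81.8%.

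**Effect of selecting.** This was simulated with 200 per arm, assumed cumulative dropout of 5/10/15%, known covariance, BIC penalty log(400) and three control-arm trends.

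- No effect: month-18 type I error is 5.3% after AIC and 4.9–5.1% after BIC. With complete data and estimated covariance it is 5.4–5.6% and 5.1–5.2%. Taking the smallest of the three p-values would give 7.2–7.4%.
- Constant −5: mean estimate −4.9 with 82% power (AIC), and −4.8 to −5.2 with 81–88% (BIC). Fixed categorical time gives −5.0 and 82%. AIC and BIC pick different forms in 55–66% of trials, and the significance verdict differs between their picks in 4–7%. The three forms do not all agree on significance in about 17% (15% with complete data).
- Waning −5, −3, 0 (an assumption): bias at month 18 is +0.1 to +0.35 mmHg, with rejection 5.5–5.8% (AIC) and 5.9–7.0% (BIC). If the plots led to a straight line, the estimate would be about −1.1 mmHg and rejection 11% (−0.5 and 7% with the stratum terms), although the true month-18 difference is zero.

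**(b) The interaction test under an exactly constant −5.** Given baseline, the follow-up covariance is 17.5² × [0.6 I + 0.24 J] = 306.25 × [0.6 I + 0.24 J]. Noncentrality = 5² × (170/2) × 3 / [306.25 × (0.6 + 3 × 0.24)] = 2125 × 3 / 404.25 = 15.8. On 3 df at the 5% level this gives 93% rejection (92.8% simulated). With the dropout pattern above it is 94% (linear), 96% (quadratic) and 95% (categorical). With equation (1)'s stratum terms it is 85–91%. The equality test beta4 = beta5 = beta6 (2 df) has noncentrality zero here and rejects in 5–6%.

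**The case against.** On (a), the endpoint, visit, contrast and three candidate forms are all named in advance. Mechanical selection keeps type I error near 5% and coverage at 93–95%, and the average estimate stays close to the truth. Criteria that pick different forms do no harm in themselves: two unbiased analyses of one dataset also disagree on significance now and then. The disagreement rate depends on the assumed profile, and with linear growth and a flat or linear control trend it is about 17%. The waning case runs against D.2's expectation of sustained improvement. Precedence between AIC and BIC could be left to a statistical analysis plan, and section C.7 gives blinded staff the judgments that knowledge of arm could bias.

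Much of this stands, and it limits the weight of (a). It does not remove the point. The protocol itself states a choice made from the outcome data and leaves it without a deciding rule. C.7 names neither the statistician nor this step.

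On (b), baseline is a modelled time point where the arm difference is held at zero, so any later difference is in that sense a change over 18 months. Read that way, the sentence is true of every non-zero effect and tells the reader nothing. It cannot support the discussion of time-dependent patterns that follows in D.2. It is fair that the test gates nothing and that the per-visit simultaneous intervals partly offset the misreading.

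**Conclusion.** Both faults hold.

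For (a), the damage to type I error is small if one criterion is applied mechanically. The weakness is an avoidable choice left open after unmasking of the outcomes: with a constant 5 mmHg benefit, the unranked criteria conflict in more than half of trials and change the significance verdict in 4–7%.

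For (b), the stated reading is wrong. A perfectly steady benefit of the planned size would be labelled time-dependent in 93–96% of trials, or 85–91% with the stratum terms. This affects secondary interpretation only.

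The figures rest on D.3's SD, correlation and attrition, and on the assumed profiles, dropout timing and covariance. The point should be corrected, but it does not by itself threaten the validity of the primary test.

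**What to change.** In section D.2:

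1. Make equation (1), with categorical time, the primary model, and prespecify its covariance. The unstructured matrix that D.2 already mentions would serve.
2. Name beta6 as the primary test. Keep linear and quadratic time as sensitivity analyses.
3. Describe the 3-df test as a test of any arm difference at 6, 12 or 18 months.
4. Test time-dependence by beta4 = beta5 = beta6 (2 df).

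The change is to wording only. The price is some power if the effect truly grows in a straight line (−1.67, −3.33, −5): 82% for categorical against 88% for linear time. Without the stratum terms, power for −5 at month 18 stays at about 82%, above the planned 80%.

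With the stratum terms entered as in equation (1), and 40% diabetes assumed, simulated power under a constant −5 is 76–77% for categorical, 72–74% for quadratic and 85–86% for linear time. All three are lower than without those terms, so the drop does not come from fixing the form of time.

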**Table 2: Summary of Study Intervention and Timeline**

TITRATED DISEASE MANAGEMENT SUPPORT (expected patients = 200, program duration of 18 months)	
Individuals randomized to the titrated disease management arm will receive medium/level 1 resource intensity [RN delivered] or high/level 2 [pharmacist delivered] disease management support depending on their level of blood pressure control. Initial assignment will be based on clinic blood pressure results over the past year. At the 6-month and 12-month study visit, disease management program intensity will be reiterated to medium/level 1 or high/level 2 resource intensity levels based on a combination of home, clinic, and study BP levels. Patients who's systolic blood pressure becomes in-control will be placed at a booster resource level [LPN delivered]. There will also be a trigger to increase resource intensity. Resource levels consist of:	
Medium/Level 1 resource intensity – RN-delivered monthly tailored telephone behavioral self-management support calls + Home BP monitoring with feedback to RN nurse educator. Based on preliminary analysis Durham VAMC patients, we expect ~130 of 200 intervention patients in this category at baseline.	
High/Level 2 resource intensity – Pharmacist delivered telephone behavioral self-management support + Home BP monitoring with feedback to pharmacist + Algorithmic medication changes directed by pharmacist (with physician backup). Based on preliminary analysis Durham VAMC patients, we expect ~70 of 200 intervention patients in this category at baseline.	
NOTE: Patients who are considered to be in control at months 6 and/or 12 (systolic BP <140 for non-diabetic and < 130 for diabetic patients)  will be moved to booster resource level [LPN-delivered telephone behavioral self-management support calls delivered approximately every 2 months].	
BOOSTER RESOURCE LEVEL CONTROL (expected patients = 200, program duration of 18 months)	
Booster Level [LPN delivered] – LPN-delivered telephone behavioral self-management support calls delivered approximately every 2 months for 18 months.	

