## **C.6. Randomization**

1. Once a patient has consented and completed the measurement battery, the patient will be randomized to one of the 2 study arms.

2. We will stratify randomization by diabetes status (because of differing hypertension treatment goals) and baseline SBP [SBP Low Strata = < 150mmHg and High Strata = SBP ≥ 150 mmHg for non-diabetic patients and Low Strata = SBP < 140mmHg and High Strata = SBP ≥ 140 mmHg for diabetic patients]. Diabetes is defined as having both: ICD 250.xx on ≥ 2 outpatient encounters during the prior year and prescription for oral hypoglycemic medication (e.g., sulfonylurea, metformin, thiazolidinedione, secretagogues, acarbose) and/or insulin during the past year. Data for the diabetes status variables will come from the data pull for evaluating inclusion/exclusion criteria and SBP is an average of study assessed readings at baseline.

3. Randomization will occur within the study computerized database. As a backup, randomization assignments by strata may be placed in sealed, consecutively numbered envelopes by a masters-level statistician before patient enrollment begins. Other similar systems for randomization, developed in consultation with study statisticians, may also be used as backup.

4. We will use blocked randomization; to prevent contamination, research assistants will be blinded to block size.

5. Patients will be told the arm to which they are assigned by the RA (or other appropriate study staff member) at the enrollment study visit. If the patient must leave the study appointment after informed consent and HIPAA Authorization have been obtained, but before randomization, the arm assignment will be revealed to the patient over the phone.

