### D.3. Sample Size and Power Considerations

The sample size estimate is based on the primary hypothesis: veterans randomized to titrated disease management will have lower mean systolic blood pressure at 18 months than veterans randomized to bi-monthly LPN-delivered telephone calls. A 5 mmHg improvement at 18 months will be the definition of a minimally clinically significant difference. This represents the differential between the two treatment groups at 18 month; therefore, the power and sample size considerations, apply even if the control group also improves over the 18 month study period (i.e., "placebo" effect). For example, if the control group improves from 145 mmHg to 142 mmHg, we will have adequate power to detect a 5 mmHg differential improvement – the intervention group improves from 145 to 137 mmHg.

Sample size calculations are based on ANCOVA methods as presented in Borm et al. We used data from previous studies to estimate quantities needed for the sample size calculation. We anticipate a common mean systolic blood pressure of 145 mmHg, a standard deviation of 17.5 mmHg in both treatment groups at baseline, and a correlation between time points equal to 0.4. Finally, based on previous studies, we estimate a 15% attrition rate by 18 months. From the calculation, we determined that **we will need to enroll until we randomize 400 patients (200 randomized in each group)** to detect a 5mmHg difference at 18 months with 80% power and a type-I error of 5%. Based on our prior recruitment experience, we consider this to be feasible given the 18 months timeframe (on average 6-7 patients per week), the potential for over 3,800 eligible individuals in Durham and a total of ~7,900 in all Durham affiliated clinics, and the requested resources. We note that these calculations do not reflect that stratification variables will be included in the final analysis model described above. Stratification variables are expected to account for variability in the outcome. The projected sample size analysis is therefore conservative, and we anticipate that there will be greater power to detect between-group differences with this study size.

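### Equation (1) holds the baseline-SBP stratum effect constant over visits although baseline SBP is itself a response, and D.3 counts that stratum as extra power

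*Protocol*

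**What the plan says.** D.2 sets out a repeated-measures model for SBP at baseline, 6, 12 and 18 months. Equation (1) has an intercept, three visit indicators and three arm-by-visit terms, with no arm main effect. The baseline reading is therefore the reference response, and the two arms share its mean. D.2 adds that the stratification "variables of baseline level of blood pressure control and diabetes status will also be included". In the equation these are single coefficients, β7 for baseline blood pressure control and β8 for diabetes, and neither varies by visit. The primary test comes from the same model: "contrasts will be written in the context of this model to test the treatment difference at month 18".

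C.6 forms the blood pressure stratum by a cut at 150 mmHg (140 mmHg with diabetes) and specifies that "SBP is an average of study assessed readings at baseline".

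D.3 sizes the trial by ANCOVA: "A 5 mmHg improvement at 18 months will be the definition of a minimally clinically significant difference", "a standard deviation of 17.5 mmHg in both treatment groups at baseline", correlation 0.4 between time points, 15% attrition, 80% power and 5% type I error, giving 400 randomised. It concludes: "Stratification variables are expected to account for variability in the outcome. The projected sample size analysis is therefore conservative".

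**The concern.** The stratum is a dichotomised version of one of the four responses. It separates patients sharply at baseline, by construction, and much less later because of regression to the mean. A coefficient forced to be equal at all visits must compromise, and the misfit goes into the residual covariance from which the 18-month standard error is computed.

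D.3 compounds this. The ANCOVA variance factor 1 − 0.4² already takes full credit for continuous baseline SBP. A cut of the same variable cannot be credited again, and as modelled it costs power. At stake is precision and an accurate statement of power, not bias or false positives.

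**Working it through.** **Inputs.** From D.3: mean 145, SD 17.5 (also used at follow-up), correlation 0.4, difference 5 mmHg, 200 per arm, 15% attrition (170 completers per arm). From C.6: cuts at 150/140. Assumed: two-sided test; 40% diabetic where a mix is needed.

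**1. D.3's own figure.** n per arm = 2(1 − ρ²)[σ(1.960 + 0.842)/δ]² = 2 × 0.84 × (17.5 × 2.802/5)² = 161.5, so 162. Then 162/0.85 = 190.6, so 191 per arm and 382 in total. At 170 completers per arm, SE = √(2 × 17.5² × 0.84/170) = √(2 × 257.25/170) = 1.740, and power = Φ(5/1.740 − 1.96) = 82.0%. D.3's 400 is thus a round-up from about 382.

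**2. Gap between strata.** Both cuts lie 5 mmHg from the mean, so z = 5/17.5 = 0.286. The strata hold 0.388 and 0.612 of each diabetes group, with p(1 − p) = 0.2374. Gap at baseline = 17.5 × 0.3830/0.2374 = 28.2 mmHg within diabetes status; at follow-up 0.4 × 28.2 = 11.3. (Pooled over diabetes status: about 27 and 11.)

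**3. Where β7 settles (unstructured covariance, large sample).** Subtracting the between-stratum part gives the within-stratum moments:
- baseline variance 306.25 − 0.2374 × 28.24² = 117.0
- baseline-follow-up covariance 122.5 − 0.2374 × 28.24 × 11.29 = 46.8
- follow-up variance 306.25 − 0.2374 × 11.29² = 276.0

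Given baseline, the follow-ups have variance 257.25 and covariance 122.5 × 0.6 = 73.5. The likelihood is maximised at β7 = 28.24 × (1/117.0)/[1/117.0 + 0.6² × 3/(257.25 + 2 × 73.5)] = 28.24 × 0.762 = 21.5. The misfit is +6.7 mmHg at baseline and −10.2 at follow-up.

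**4. Reported SE.** The fitted covariance absorbs the misfit:
- baseline variance 117.0 + 0.2374 × 6.72² = 127.7
- covariance 46.8 − 0.2374 × 6.72 × 10.22 = 30.5
- follow-up variance 276.0 + 0.2374 × 10.22² = 300.8

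Equation (1): 300.8 − 30.5²/127.7 = 293.5, so SE = √(2 × 293.5/170) = **1.858**. Stratum by visit: 276.0 − 46.8²/117.0 = 257.25, so SE = **1.740**. The interval is 6.8% wider.

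**5. Actual SE and power.** Stratified randomisation balances the strata, so the misfit does not add to the true variance. With the model's weight 30.5/127.7 = 0.239 on baseline, that variance is 276.0 − 2 × 0.239 × 46.8 + 0.239² × 117.0 = 260.3, SE 1.750. Power = Φ[(5 − 1.96 × 1.858)/1.750] = 78.1%, against 82.0%. Type I error = 2Φ(−1.96 × 1.858/1.750) = 3.7%.

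**6. Simulation, including the other named covariance and an enrolment floor.** Equation (1) against the same model with stratum and diabetes by visit; 8,000 trials, covariance at its large-sample value, power by normal approximation:

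| Baseline population | Covariance | SE, eq. (1) | SE, by visit | Wider | Power |
|---|---|---|---|---|---|
| D.3 inputs | unstructured | 1.857 | 1.735 | 7.0% | 78.4 vs 82.4% |
| D.3 inputs | random intercept-slope | 1.878 | 1.778 | 5.6% | 77.8 vs 81.0% |
| Truncated at 140/130 | unstructured | 1.803 | 1.742 | 3.5% | 80.1 vs 82.0% |
| Truncated at 140/130 | random intercept-slope | 1.836 | 1.795 | 2.3% | 79.0 vs 80.3% |
| Truncated, 35% high stratum | unstructured | 1.814 | 1.738 | 4.4% | 79.8 vs 82.1% |
| Truncated, 35% high stratum | random intercept-slope | 1.833 | 1.792 | 2.3% | 79.1 vs 80.4% |

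The truncated rows follow C.23, where a patient "cannot be enrolled because he or she has baseline blood pressure indicate hypertension is in control". The 35% follows Table 2 for the high level: "we expect ~70 of 200 intervention patients in this category at baseline". Full maximum likelihood with unstructured covariance (4,000 trials) agrees: on D.3 inputs power is 78.3% against 82.1%; truncated, 79.4% against 82.0%. Type I error under equation (1) was 3.1-4.1%.

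**7. What the stratifiers can add.** With stratum by visit and unstructured covariance, the SBP stratum changes the SE by 0.0% compared with leaving it out. If diabetes status shifts 18-month SBP by d beyond baseline SBP, the residual variance is 257.25 − 0.4 × 0.6 × d². For d = 0, 3, 5, 8 mmHg (assumed range), power is 82.0, 82.3, 82.8 and 84.2%.

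**The case against.** - **The estimator is hardly worse.** True: 1.750 against 1.740 in step 5. The loss comes through an overstated standard error. But the test uses that standard error, so the power loss is real. A standard sandwich variance does not cure it: in a check it equalled the model SE. It treats patients as independent draws and so also counts the misfit that stratified randomisation has balanced out.
- **The 6-7% comes from a population the trial would not enrol.** Fair. A normal distribution with mean 145 and SD 17.5 puts 39% of non-diabetic patients below 140 and 20% of diabetic patients below 130. The truncated cases give 2-4%. One baseline shape close to the protocol's figures (mean 146, SD 11.2, 37% high stratum) gives only 1.8% unstructured (81.3 against 82.3% power) and 1.0% random intercept-slope (79.1 against 79.7%). In the other direction, a comparison with no stratum term at all under random intercept-slope, on D.3 inputs, reaches 8.9% and about 5 points.
- **Equation (1) is one of several options, and section D allows methods to change.** The choices D.2 leaves open concern time by treatment group and the covariance. None makes the stratum effect vary by visit. The finding applies to the equation as printed.
- **D.3 speaks of the stratifiers jointly, and 400 does exceed its formula.** Correct. Diabetes status may help, and the round-up is real slack. The stated reason fails for the SBP stratum only.

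**Conclusion.** The point holds. As printed, equation (1) makes the 18-month interval about 2-7% too wide and costs about 1-4 power points under the two covariance structures D.2 names. Power is about 78% on D.3's inputs and 79-80% with an enrolment floor, at or just under the stated 80%. The estimate is unbiased and the test slightly conservative. D.3's claim of conservatism is wrong for the SBP stratum. What slack exists comes from rounding about 382 up to 400, and possibly from diabetes status.

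The size rests on assumptions outside the protocol: 40% diabetic, follow-up SD 17.5, the shape of the baseline distribution, and dropout unrelated to outcome. The direction was the same in every scenario under the named structures. A random-intercept-only covariance, which D.2 does not name, would reverse it (model SE 4.5-11% too small, type I error 5.9-8.2%), and visit interactions would not repair that. The correction is worth making but does not threaten the trial's validity.

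**What to change.** In D.2, let baseline BP control and diabetes interact with visit in equation (1), and specify an unstructured covariance. Either of two alternatives also removes the problem:
- drop the baseline BP control term while baseline SBP stays a response; this takes a randomisation stratifier out of the model, although continuous baseline SBP still carries its information;
- model SBP at 6, 12 and 18 months with continuous baseline SBP as a covariate.

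In D.3, remove the SBP stratum from the conservatism argument, attribute any extra power to diabetes status and to the round-up to 400, and state power of about 82% at 170 completers per arm.

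The cost is wording in two sections and, for the interaction version, six more coefficients (two terms at three follow-up visits). Sample size, data collection and conduct are unchanged.
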